#### 7.9 TREATMENT COMPLIANCE

The local trial pharmacist will be responsible for maintaining and updating the drug accountability log in the study pharmacy file, which will be used to monitor compliance. All unfinished packs will be returned to the trial pharmacist who will count and document any unused medication. All IMP can then be destroyed in accordance with local pharmacy practice and this will be documented on the drug destruction log in the hospital pharmacy file.

# 7.10 BEST SUPPORTIVE THERAPY

All patients will receive best supportive therapy for COVID-19 as per physician's discretion.

# 7.11 PERMITTED CONCOMITANT THERAPY REQUIRING CAUTION AND/OR ACTION

Patients may receive anti-emetics, calcineurin inhibitors, azole fungal prophylaxis or broad-spectrum antibiotics (either semi-synthetic penicillin or third generation cephalosporin with vancomycin, gentamycin or equivalent). Use of sedatives should be closely monitored for potential drug-drug interaction effects. Use of oral, injected or implanted hormonal methods of contraception are allowed while on ruxolitinib. Ruxolitinib dose adjustments may be required, particularly in patients treated with CYP450 modulators.

# 7.12 STRONG CYP3A4 INHIBITORS OR DUAL CYP3A4/CYP2C9 INHIBITORS

Upon initiation of a strong CYP3A4 inhibitor, including clarithromycin or a dual CYP3A4/CYP2C9 inhibitor including fluconazole up to a dose of 200 mg, suggest change antibiotic to azithromycin or doxycycline. If patient must remain on a strong CYP3A4 inhibitor or dual CYP3A4/CYP2C9 inhibitor, then the dose of ruxolitinib should be reduced (e.g. by 50%) with daily monitoring of haematology parameters and clinical signs and symptoms of ruxolitinib related adverse events. In the event of suspected study drug related toxicity or overdose; administration of ruxolitinib should be dose reduced or held according to the treating physician's judgement. Ideally an alternative therapy should be sourced rather than reduce the dose of ruxolitinib. For additional information, please refer to the ruxolitinib summary of product characteristics (SmPC).

IRAS: 282552 Page **38** of **57** 

Imperial College Healthcare NHS Trust

#### 7.13 PROHIBITED MEDICATION

The following medications are prohibited until treatment discontinuation:

- Concomitant use of another JAK inhibitor

For additional information, please refer to the ruxolitinib SmPC.

# 7.14 CONCOMITANT MEDICATION

The metabolism of ruxolitinib is affected by CYP3A4 inducers and inhibitors and dual inhibitors of CYP2C9 and CYP3A4 enzymes. Strict attention to this detail is required; please refer to permitted and prohibited concomitant medication as detailed in the SmPC. Patients should not receive any other JAK2 inhibitor whilst on the trial.

All medications, procedures, and significant non-drug therapies (including physical therapy and blood product support) administered after the participant was enrolled into the study must be recorded on the Case Report Forms. Each concomitant drug must be individually assessed against all exclusion criteria/prohibited medication.

# 7.15 SUPPLY OF STUDY TREATMENT

Ruxolitinib will be provided free of charge by Novartis at the following strengths: 5 mg, 10 mg, and 20 mg. Each tablet contains 5 mg, 10mg, or 20mg ruxolitinib (as phosphate). The tablets should not be stored above 30°C. PVC/PCTFE/Aluminium blister packs containing 14 or 56 tablets or multipacks containing 168 (3 packs of 56) tablets.

Fostamatinib will be provided free of charge by Rigel at the following strengths: 100 mg and 150 mg. Each film-coated tablet contains either 126.2 mg or 189.3mg of fostamatinib disodium hexahydrate equivalent to 100 mg and 150mg of fostamatinib respectively. This medicinal product does not require any special temperature storage conditions. It should be stored in the original package to protect from moisture and keep the bottle tightly closed.

The local trial pharmacist will be responsible for maintaining and updating the drug accountability log in the MATIS pharmacy file which will be used to monitor compliance. All unfinished bottles will be returned to the trial pharmacist who will count and document any unused medication. All IMPs can then be destroyed in accordance with local pharmacy practice and this will be documented on the drug destruction log in the hospital pharmacy file

MATIS version 4.0 dated 2nd November 2022

IRAS: 282552 Page **39** of **57** 

Imperial College Healthcare

#### 7.16 TREATMENT DURATION

The planned duration of treatment is 14 days. Participants may be discontinued from treatment earlier due to unacceptable toxicity or disease progression which will be recorded as Serious Adverse Event (SAE). If participant is being discharged prior to day 14 they will go home and continue with the treatment plan.

# 8 PHARMACOVIGILANCE

#### 8.1 DEFINITIONS

Adverse Event (AE): any untoward medical occurrence in a patient or clinical trial subject administered a medicinal product and which does not necessarily have a causal relationship with this treatment. An AE can therefore be any unfavourable and unintended sign (including an abnormal laboratory finding), symptom, or disease temporally associated with the use of an investigational medicinal product (IMP), whether or not considered related to the IMP.

Adverse Reaction (AR): all untoward and unintended responses to an IMP related to any dose administered. All AEs judged by either the reporting investigator or the sponsor as having reasonable causal relationship to a medicinal product qualify as adverse reactions. The expression reasonable causal relationship means to convey in general that there is evidence or argument to suggest a causal relationship.

**Unexpected Adverse Reaction:** an AR, the nature or severity of which is not consistent with the applicable product information (e.g. investigator's brochure for an unapproved investigational product or SmPC for an authorised product). When the outcome of the adverse reaction is not consistent with the applicable product information this adverse reaction should be considered as unexpected. Side effects documented in the SmPC which occur in a more severe form than anticipated are also considered to be unexpected.

**Serious Adverse Event (SAE)** or **Serious Adverse Reaction (SAR):** any untoward medical occurrence or effect that at any dose:

- Results in death.
- Is life-threatening refers to an event in which the subject was at risk of death at the time of the event; it does not refer to an event which hypothetically might have caused death if it were more severe.
- Requires hospitalisation, or prolongation of existing inpatients' hospitalisation.
- Results in persistent or significant disability or incapacity.
- Is a congenital anomaly or birth defect.

Medical judgement should be exercised in deciding whether an AE/AR is serious in other situations. Important AE/ARs that are not immediately life-threatening or do not result in death or hospitalisation but may jeopardise the subject or may require intervention to prevent one of the other outcomes listed in the definition above, should also be considered serious.

**Suspected Unexpected Serious Adverse Reaction (SUSAR):** any suspected adverse reaction related to an IMP that is both unexpected and serious.

# 8.2 CAUSALITY

Most adverse events and adverse drug reactions that occur in this study, whether they are serious or not, will be expected treatment-related toxicities due to the drugs used in this study. The assignment of the causality should be made by the investigator responsible for the care of the participant using the definitions in the table below. If any doubt about the causality exists, the local investigator should inform the study coordination centre who will notify the Chief Investigators. The pharmaceutical companies and/or other clinicians may be asked to advise in some cases. In the case of discrepant views on causality between the investigator and others, all parties will discuss the case. In the event that no agreement is made, the MHRA will be informed of both points of view.

**Table 6. Defining causality** 

Relationship	Description
Unrelated	There is no evidence of any causal relationship
Unlikely	There is little evidence to suggest there is a causal relationship (e.g. the event did not occur within a reasonable time after administration of the trial medication). There is another reasonable explanation for the event (e.g. the participant's clinical condition, other concomitant treatment).
Possible	There is some evidence to suggest a causal relationship (e.g. because the event occurs within a reasonable time after administration of the trial medication). However, the influence of other factors may have contributed to the event (e.g. the participant's clinical condition, other concomitant treatments).
Probable	There is evidence to suggest a causal relationship and the influence of other factors is unlikely.
Definitely	There is clear evidence to suggest a causal relationship and other possible contributing factors can be ruled out.
Not	There is insufficient or incomplete evidence to make a clinical judgement of the causal
assessable	relationship.

IRAS: 282552 Page **41** of **57** 

Imperial College Healthcare

#### 8.3 SAE GRADING

Grade 1: Mild; asymptomatic or mild symptoms; clinical or diagnostic observations only; intervention not indicated.

Grade 2: Moderate; Minimal, local, or non-invasive intervention indicated; limiting age appropriate instrumental activities of daily living (ADL).

Grade 3: Severe or medically-significant but not immediately life-threatening; hospitalisation or prolongation of hospitalisation indicated; disabling; limiting self-care ADL.

Grade 4: Life-threatening consequences; urgent intervention indicated.

Grade 5: Death related to AE.

#### 8.4 REPORTING PROCEDURES

All adverse events should be reported. Depending on the nature of the event the reporting procedures below should be followed. Any questions concerning adverse event reporting should be directed to the study coordination centre in the first instance. A flowchart is given below to aid in the reporting procedures.

#### Non serious AR/AEs

All such toxicities, whether expected or not, should be recorded in the toxicity section of the relevant case report form and sent to the study coordination centre within one month of the form being due.

#### **Serious AR/AEs**

Fatal or life-threatening SAEs and SUSARs should be reported on the day that the local site is aware of the event. The SAE form asks for nature of event, date of onset, severity, corrective therapies given, outcome and causality (i.e. unrelated, unlikely, possible, probably, definitely). The responsible investigator should sign the causality of the event. Additional information should be sent within 5 days if the reaction has not resolved at the time of reporting.

#### **SAEs**

An SAE form should be completed and faxed to the study coordination centre for all SAEs within 24 hours. However, relapse and death due to <condition>, and hospitalisations for elective treatment of a pre-existing condition do not need reporting as SAEs.

#### **SUSARs**

In the case of suspected unexpected serious adverse reactions, the staff at the site should:

Complete the SAE case report form & send it immediately (within 24 hours, preferably by fax), signed and dated to the study coordination centre together with relevant treatment forms and anonymised copies of all relevant investigations.

Or

Contact the study coordination centre by phone and then send the completed SAE form to the study coordination centre within the following 24 hours as above.

The study coordination centre will notify the MHRA, REC and the Sponsor of all SUSARs occurring during the study according to the following timelines; fatal and life-threatening within 7days of notification and non-life threatening within 15 days. All investigators will be informed of all SUSARs occurring throughout the study. Local investigators should report any SUSARs and /or SAEs as required by their Local Research Ethics Committee and/or Research & Development Office.

#### 8.5 COVID-19 CONSIDERATIONS

#### **Recording Suspected Serious Adverse Reactions**

The focus is on those events that, based on a single case, are highly likely to be related to the study medication. Examples include anaphylaxis, Stevens Johnson Syndrome, or bone marrow failure, where there is no other plausible explanation. Any SAE that is believed with a reasonable probability to be due to one of the study treatments will be considered a Suspected Serious Adverse Reaction (SSAR). In making this assessment, there should be consideration of the probability of an alternative cause (for example, COVID-19 itself or some other condition preceding randomisation), the timing of the event with respect to study treatment, the response to withdrawal of the study treatment, and (where appropriate) the response to subsequent re-challenge. All SSARs should be reported by telephone to the Central Coordinating Office and recorded on the study IT system immediately.

# Central assessment and onward reporting of SUSARs

Clinicians at the Central Coordinating Office are responsible for expedited review of reports of SSARs received. Additional information (including the reason for considering it both serious and related, and relevant medical and medication history) will be sought. The focus of SUSAR reporting will be on those events that, based on a single case, are highly likely to be related to the study medication. To this end, anticipated events that are either efficacy endpoints, consequences of the underlying disease, or common in the study population will be exempted from expedited reporting. Thus, the following events will be exempted from expedited reporting:

(i) Events which are the consequence of COVID-19; and

IRAS: 282552 Page **43** of **57** 

(ii) Common events which are the consequence of conditions preceding randomisation.

Any SSARs that are not exempt will be reviewed by a Central Coordinating Office clinician and an assessment made of whether the event is "expected" or not (assessed against the relevant Summary of Product Characteristics or Investigator Brochure). Any SSARs that are not expected would be considered a Suspected Unexpected Serious Adverse Reaction (SUSAR). All confirmed SUSARs will be reported to the Chair of the DMC and to relevant regulatory authorities, ethics committees, and investigators in an expedited manner in accordance with regulatory requirements.

# **Recording other Adverse Events**

[figure not shown]
In addition to recording Suspected Serious Adverse Reactions, information will be collected on all deaths and efforts will be made to ascertain the underlying cause. Other non-serious adverse events will not be recorded. It is anticipated that for some sub-studies, more detailed information on adverse events (e.g. through linkage to medical databases) or on other effects of the treatment (e.g. laboratory or radiological features) will be recorded and analysed but this is not a requirement of the core protocol.

IRAS: 282552 Page **44** of **57** 

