#### **Secondary endpoints**

Comparison of the incidence, time-to-event, median or odds ratio of each of the parameters below at 14 and 28 days between RUX or FOS versus SOC:

- Mortality
- Invasive ventilation
- Non-invasive ventilation including CPAP and high flow nasal oxygen
- Renal replacement therapy
- Venous thromboembolism
- Inflammatory markers CRP, LDH, ferritin, D-dimer
- Serum creatinine
- Length of stay
- SSARs and discontinuations of study arms
- Change in severity on the modified WHO COVID-19 Ordinal Scale

Comparison of the incidence, time-to-event, median or odds ratio of each of the parameters below:

- Mortality at 3, 6, 12 & long term outcome
- Venous thromboembolism rate at 6, 12 and 18 months
- Renal replacement therapy at 6, 12 and 18 months
- Occurrence of new hypertension diagnosis
- Occurrence of new diabetes diagnosis
- Number of re-admissions within 12 months
- Causes of re-admissions in the last 12 months
- Occurrence of lung fibrosis
- Co-morbidities developed within 18 months post-discharge from hospital

Further secondary and exploratory objectives are not the focus of this study but maybe adopted using routine healthcare records (e.g. NHS Digital) and relevant research studies (e.g. UK Biobank and Genomics England). This will allow subsidiary analyses of the effect of the study treatments on particular non-fatal events (e.g. ascertained through linkage to Hospital Episode Statistics), the influence of pre-existing major co-morbidity (e.g. chronic heart, lung, kidney, liver disease, diabetes and use of immunosuppressive drugs) and longer-term outcomes (e.g. 6 month survival) as well as in particular sub-categories of patient (e.g. by genotype).

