11.4 DATA AND SAFETY MONITORING

Follow-up safety assessment will occur at day 7, 14 and 28 days. Serious adverse events (SAEs) will be collected and reported in an expedited fashion. The requirements for collection of AEs is as follows:

All SAEs

All non-serious AEs

All reports of IMP exposure during pregnancy

• All reports of misuse and abuse of an IMP, other medication errors and uses outside of what is foreseen in the protocol (irrespective if a clinical event has occurred

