2.8 Serious adverse events

Incidence of venous thromboembolism and serious adverse events will be collected in this study to assess safety.

The proportion of participants experiencing a venous thromboembolism will be summarised by treatment arm and summaries of the time since randomisation will be presented. The number of readmissions will also be extracted from free text in SAE reports and will be summarised by treatment arm.

Serious adverse events coded as per the CTCAE will be summarised at the preferred term level and body system class. Events will be tabulated by treatment arm including information on the number with at least one event and the number of events to account for recurrent events.

Raw data for each SAE will be listed with information on event type, timing duration and outcome.

All above analysis will be undertaken for stage I and stage II

For stage II analysis we will also undertake the following analysis:

In addition, incident rate ratios for each event between treatment arms (RUX vs SOC or FOS vs SOC) with corresponding 95% CI will be calculated to account for differential follow-up and recurrent events with 95% CIs using a suitable model e.g. a negative binomial model or ZIP as appropriate. These results will be presented in both a table and graphically using a dot plot.

For events where time-to-event analysis is deemed appropriate we will present Kaplan-Meier plots with extended at risk tables for events that occur once within participants and mean cumulative function plots where events can recur within participants.^{1,2}

Blood measurements will be analysed as continuous outcomes calculating a mean difference and 95% CIs over the study follow-up period using a linear mixed effect model and the between arm effect will be plotted over time. Participants will be included as a random intercept with fixed effects for treatment arm, time and baseline outcome values. Stratification variables age and site, plus receipt of known effective treatments dexamethasone and/or tociluzimab, prior vaccination against COVID-19 and receipt of paxlovid and/or molnupiravir at the time of or prior to randomisation into MATIS will also be included as fixed effects. These outcomes will also be categorised as abnormal/normal and analysed using the distributional approach to retain power at day 14 and 28.3

3. Data analysis plan - Inferential analysis

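### The SSAR comparison with SOC is zero in SOC by construction, and the protocol's rules on which adverse events to record conflict or leave gaps

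*Protocol*

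**What the plan says.** **Safety endpoint.** Protocol 3.3 includes "SSARs and discontinuations of study arms" among the parameters compared at 14 and 28 days between RUX or FOS and SOC. Section 8.5 defines an SSAR as an SAE believed, with reasonable probability, to be caused by one of the study treatments, and adds: "The focus is on those events that, based on a single case, are highly likely to be related to the study medication". Section 5.3 spells out study treatment as FOS or RUX.

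**Non-serious events.** Section 8.4 opens by asking for every adverse event to be reported. For non-serious ones it says: "All such toxicities, whether expected or not, should be recorded in the toxicity section of the relevant case report form". Section 11.4 lists "All non-serious AEs" as required collection. Section 8.5, under Recording other Adverse Events, says: "Other non-serious adverse events will not be recorded". The schedule in Table 7 has a row for serious adverse events only.

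**Serious events.** Section 8.4 wants an SAE form for all SAEs within 24 hours, but then exempts: "relapse and death due to <condition>, and hospitalisations for elective treatment of a pre-existing condition do not need reporting as SAEs". Section 8.5 speaks of recording SSARs and collecting information on all deaths. Section 7.16, repeated in SAP 1.4.5, says patients may stop treatment early for "unacceptable toxicity or disease progression which will be recorded as Serious Adverse Event (SAE".

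**Analysis.** SAP 2.8 tabulates SAEs and venous thromboembolism by arm and plans "incident rate ratios for each event between treatment arms (RUX vs SOC or FOS vs SOC". It takes the number of readmissions from free text in SAE reports. SAP 1.1.3 lists readmission within 28 days as a secondary outcome from that source.

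**The concern.** Three things look wrong together.

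- A secondary endpoint is defined so that the control arm cannot contribute to it, yet it is listed for comparison with control.
- Sites are told in two places to record non-serious events and in a third not to, so the non-serious data will depend on which section a site followed.
- The scope of SAE recording is not closed. The exemption for deaths names no disease. The COVID-specific section is silent on non-fatal SAEs judged unrelated to study drug. One route by which progression becomes an SAE runs through stopping a drug that SOC patients never take.

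The trial is open label, so whoever fills in the form knows the arm. The SAP's between-arm SAE ratios and readmission summary are sound only if SAEs are captured in the same way in all three arms. The protocol should settle that in its text.

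**Working it through.** This is mainly a reading of the sections against each other. The documents state no safety event rate, SSAR count or safety power, so there is no plan figure to reproduce.

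**Step 1: the SSAR contrast.**
- An SSAR requires attribution to a study treatment (8.5).
- Study treatment means FOS or RUX (5.3).
- A SOC patient given neither drug therefore has zero SSARs by definition.
- SSARs appear in neither SAP outcome list (1.1.3, 3.2), and SAP 2.8 uses SAEs with no causality filter. Protocol and SAP therefore name different safety variables.

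*Illustration only.* Take the maximum arm size, 57 + 95 = 152, and a drug that causes no harm. Assume an SAE rate s of 10% to 30%, and that a share a of 5% to 20% of those SAEs is attributed to the drug. Neither range is in the documents.

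Expected SSARs in a drug arm = 152 × s × a:
- Low end: 152 × 0.10 × 0.05 = 0.76
- Middle: 152 × 0.20 × 0.10 = 3.04
- High end: 152 × 0.30 × 0.20 = 9.12

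SOC has 0 in every case. With 152 per arm, 5 against 0 gives a two-sided Fisher p of 0.060, and 6 against 0 gives 0.030. The binomial chance of 6 or more in the drug arm is below 0.1%, 8.6% and 90% in the three cases. A significant SSAR difference could thus come from attribution alone, and it could only point one way. The SAP does not plan this test; it is used here only to show the behaviour of the contrast.

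**Step 2: non-serious events.**

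| Place in protocol | Non-serious AEs |
|---|---|
| 8.4, opening and Non serious AR/AEs | Record on the case report form |
| 11.4 | Collect |
| 8.5, Recording other Adverse Events | Do not record |
| Table 7 | No row; serious events only |

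The first two rows and the third cannot all be followed.

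**Step 3: serious events.**

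| Place | SAE rule | What is left open |
|---|---|---|
| 8.1 and 8.4 | All SAEs, with no limit by arm or causality | Which deaths the exemption covers, because its field is empty |
| 8.5 | Names SSARs and all deaths | Whether non-fatal, unrelated SAEs are still recorded as in 8.4 |
| 7.16, SAP 1.4.5 | Toxicity or progression that stops treatment is recorded as an SAE | How progression is recorded in SOC, which has no study drug to stop |
| 11.4, Table 7 | SAEs collected, and scheduled at each visit | – |

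Section 8.5 excludes only non-serious events in so many words. It neither repeats nor withdraws the all-SAE rule.

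**Step 4: what depends on this.** The rate ratios and the readmission summary in SAP 2.8 both draw on SAE reports. Uneven capture between sites or arms would pass into both. Its size would depend on how many SAEs go unreported in each arm, for which the documents give no figure.

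**The case against.** The strongest reply is that the planned safety analysis is the one in SAP 2.8: all SAEs and venous thromboembolism by arm, without regard to attribution. That analysis has no structural zero. Hospitalisation, prolonged stay, danger to life and death are SAE criteria in 8.1 for any patient. Section 8.4 asks for a form for all SAEs, 11.4 lists all SAEs, and Table 7 schedules them at every visit without limit by arm. Section 7.16 does not say that progression without a treatment stop goes unrecorded. The reporting exemptions under Central assessment and onward reporting of SUSARs in 8.5 are expressly from expedited reporting. The conflict over non-serious events touches no planned ratio, because SAP 2.8 does not analyse them as adverse events. Figure 3, the safety reporting flowchart, is not visible in the text reviewed and may show how 8.4 and 8.5 fit together.

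Most of this stands, and it limits the point. A reader might infer that the RUX or FOS versus SOC safety comparison as a whole is biased, or that 7.16 makes progression an SAE in the drug arms only. The documents do not support either reading, because the general SAE definition and the all-SAE rule already cover SOC. A reader might also see a conflict between same-day reporting of fatal or life-threatening SAEs and the 24-hour limit for SAEs in general. That is a tiered timeline.

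The reply leaves three defects in place: the SSAR endpoint, the contradiction on non-serious events, and the unfilled exemption beside a section that does not say the all-SAE rule survives.

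**Conclusion.** The point holds in three parts.

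1. The SSAR part of the protocol endpoint cannot support its stated comparison with SOC. The count in SOC is zero by construction, barring off-protocol use of RUX or FOS. The other part of that endpoint, discontinuations, is not covered by this finding.
2. The rules on non-serious adverse events contradict each other as written.
3. The SAE rules are incomplete: an empty exemption field, a COVID-specific section that does not restate the all-SAE rule, and a progression clause tied to stopping study drug. This leaves the SAP's SAE rate ratios and readmission summary open to uneven recording in an open-label trial. It does not show that they are biased.

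No size can be given for part 3 from the documents. The range of 0.8 to 9.1 SSARs against 0 in part 1 rests wholly on the assumed SAE and attribution rates. Parts 1 and 2 rest on plain text. Confidence about what sites were actually told on SAEs is lower, because Figure 3 could not be read.

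**What to change.** - **3.3:** for the comparison with SOC, replace SSARs with SAEs irrespective of causality, in line with SAP 2.8. Keep SSARs as a listing within the drug arms.
- **8.5:** state that all SAEs in all three arms are recorded as section 8.4 requires, and that the exemptions in 8.5 apply to expedited reporting only.
- **8.4:** replace the empty template field with an explicit statement of which deaths and events, if any, are exempt.
- **7.16 and SAP 1.4.5:** reconcile with 8.4, so that COVID-19 progression and death are recorded in the same way in every arm, whether or not study drug is stopped.
- **8.4, 8.5, 11.4 and Table 7:** give one statement on whether non-serious adverse events are recorded, and delete the text that contradicts it. Check Figure 3 against the result.

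The cost is a wording amendment, a note to sites, and possibly a few more SAE forms from SOC patients. The SAE form and the SAP analysis already exist.
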